**Note: The Type of Submission cannot be changed after this application has been submitted for review.**

4 Original Version #:

ID: VIEW4DF8709A33C00  
Name: v2\_Introduction Page

## Resources

If this study is a collaborative UM/VA study, please clarify which resources are being used at each institution.

- 1    \* **Describe the time that the Principal Investigator will devote to conducting and completing the research:**  
[name] will devote approximately 20% effort toward conducting and completing this research.
- 2    \* **Describe the facilities where research procedures are conducted:**  
This research will be conducted at the University of Maryland, the Amish Research Clinic, and at the participants' homes. The Amish Research Clinic is located in Lancaster, PA. It consists of over 3,300 square feet of clinical, examining/procedure rooms, and fully equipped clinical laboratory for sample processing and storage. For fieldwork, there are 5 vans and a recreational vehicle outfitted to do clinics in the community.
- 3    \* **Describe the availability of medical and/or psychological resources that subjects might need as a result of anticipated consequences of the human research:**  
There are no significant psychological negative effects expected as a consequence of research participation. Research staff are trained in the management of complications. The Principal Investigator and physician co-investigators are available to manage adverse events related to the study.
- 4    \* **Describe the process to ensure that all persons assisting with the research are adequately informed about the protocol, the research procedures, and their duties and functions:**  
All of the research team members are oriented to the protocol procedures and responsibilities according to their respective roles on the project. They will review the IRB-approved protocol and associated documents and will participate in a series of team and individual study meetings appropriate to key research team members.

ID: V1EW4DF83CB976400  
Name: v2\_Resources

HP-00081981

Sites Where Research Will Be Conducted\_V2

## Funding Information

1 \* Indicate who is funding the study:

- Federal**
- Industry
- Department / Division / Internal
- Foundation
- Private
- State Agency

2 \* What portion of the research is being funded? (Choose all that apply)

- Drug
- Device
- Staff**
- Participant Compensation**
- Procedures**
- Other

3 Please discuss any additional information regarding funding below:

ID: VIEW4DF85DF452400  
Name: V2\_Funding Information

HP-00081981

DHHS Funded Study\_V2

## DHHS Funded Study

You indicated that this is a Federally funded study.

1 \* Is this study sponsored by a Department of Health and Human Services (DHHS) agency?

Yes  No

2 You may upload any grant documents here:

Name	Created	Modified Date
 KCNQ1 R21(0.01)	7/17/2018 3:22 PM	7/17/2018 3:22 PM

ID: V1EW4DF87B9560800  
Name: v2\_DHHS Funded Study

HP-00081981

Federal Agency Sponsor Contact Information\_V2

**Grant Number 1 (if applicable):**

- OR - Check here if Grant 1 is not assigned a number.

**If Grant 1 has no number, please provide the following information:**

**Title of Grant 1:**

A Community-Based Approach to Overcoming Barriers to Cascade Screening for Long QT Syndrome

**Grant Number 2 (if applicable):**

- OR - Check here if Grant 2 is not assigned a number.

**If Grant 2 has no number, please provide the following information:**

**Title of Grant 2:**

**PI of Grant 2:**

**Grant Number 3 (if applicable):**

- OR - Check here if Grant 3 is not assigned a number

**If Grant 3 has no number, please provide the following information:**

**Title of Grant 3:**

**PI of Grant 3:**

**Grant Number 4 (if applicable):**

- OR - Check here if Grant 4 is not assigned a number.

**If Grant 4 has no number, please provide the following information:**

**Title of Grant 4:**

## PI of Grant 4:

ID: VIEW4DF8584874400  
Name: v2\_Federal Agency Sponsor Information

HP-00081981

Research Protocol\_V2

## Research Protocol

1 \* Do you have a research protocol to upload?

Yes

No, I do not have a research protocol and will use the CICERO application to enter my study information

2 If Yes, upload the research protocol:

**Name**

**Created**

**Modified Date**

There are no items to display

ID: VIEW4E00563F8D000  
Name: v2\_Research Protocol

HP-00081981

Risk Level\_V2

## Risk Level

**What is the risk level of your study? (Ultimately, the IRB will determine the appropriate risk level and your designation is subject to change.)**

\* Choose One:

- Minimal - The probability & magnitude of harm/discomfort anticipated in the research are not greater in and of themselves than those ordinarily encountered in daily life or during the performance of routine physical or psychological examinations/tests.
- Greater Than Minimal - Does not meet the definition of Minimal Risk.

ID: VIEW4E02805225800  
Name: v2\_Risk Level

HP-00081981

Type of Research\_V2

## Type of Research

1 \* Indicate **ALL** of the types of research procedures involved in this study (Choose all that apply):

- Use of unapproved drug(s)/biologic(s) or approved drug(s)/biologic(s) whose use is specified in the protocol.
- Evaluation of food(s) or dietary supplement(s) to diagnose, cure, treat, or mitigate a disease or condition.
- Use of device(s) whose use is specified in the protocol
- Psychological/Behavioral/Educational Method or Procedure (i.e., survey, questionnaires, interviews, focus groups, educational tests).
- Sample (Specimen) Collection and/or Analysis (including genetic analysis).
- Data Collection or Record Review (i.e., chart review, datasets, secondary data analysis).
- None of the above.

2 \* Is this study a clinical trial OR will this study be registered at ClinicalTrials.gov?

A clinical trial is a research study in which one or more human subjects are prospectively assigned to one or more interventions (which may include placebo or other control) to evaluate the effects of those interventions on health-related biomedical or behavioral outcomes.

Yes  No

ID: VIEW4E0280569E000  
Name: v2\_Type of Research

HP-00081981

Lay Summary\_V2

## Lay Summary

**1 \* Provide a summary of the background and purpose of the study in language that can be understood by a person without a medical degree.**

The Amish Complex Diseases Research Program of the University of Maryland identified a mutation in the KCNQ1 gene, a gene known to cause Long QT Syndrome (LQTS). LQTS is associated with an increased risk of fainting (syncope) and sudden death. Beta blocker medications have been shown to reduce the risk of syncope and sudden death in LQTS by 70-90%. Therefore, identifying a mutation known to cause LQTS can lead to treatment that significantly reduces an individual's risk of serious cardiac events.

The KCNQ1 gene mutation is common in the Amish, present in 1/45 individuals as opposed to the general population where mutations in KCNQ1 are seen in about 1/2000. Of 5988 Amish individuals who have participated in our research studies carried out over the past 20 years, 140 of them have this KCNQ1 variant. To date, 88 individuals have participated in a return of results study (referred to here as "ROR" study) for clinical confirmation of the mutation, collection of clinical information, genetic counseling, and recommendations for treatment. Genetic counseling includes recommendations for all first degree relatives (who are at 50% risk of having the KCNQ1 mutation) to undergo genetic screening. This is known as "cascade testing". Cascade testing would involve going to the Clinic for Special Children and obtaining the genetic test via a blood sample for \$50 per test. Identifying family members who are positive for the KCNQ1 mutation would allow counseling for treatment recommendations to help prevent future cardiac events. It is known that very few family members of mutation carriers do cascade testing, but the reasons for this are not completely known. Inconvenience and cost are felt to be some of the important reasons.

The current study will evaluate the ethical, legal and social impacts of patients receiving genetic results and will assess whether providing free genetic testing in a very convenient manner (in-home, saliva collection) will improve uptake of cascade testing.

Aim 1: Individuals who participated in the ROR study (probands) and their first degree blood-related family members will be invited to participate. All probands will be mailed a consent letter describing the intervention, a survey, a response card and a copy of the family invitation letter. With the probands permission, invitation letters will be mailed to their first degree relatives to offer study participation including free, saliva-based genetic testing and completion of surveys. The proband can decide to enroll their minor children who still live at home in the cascade screening.

Our primary outcome addresses the question of whether our simplified cascade screening intervention improves uptake of screening. Our secondary outcomes assess whether, with access to simplified screening (1) probands will tell more family members- who may or may not choose to get screened, (2) informed family members are more likely to get tested, and (3) identifying more individuals with the KCNQ1 variant actually results in more beta-blocker prescriptions since the Amish typically take very few prescription medications. We will compare these outcomes before the implementation of our intervention (the 'traditional' cascade screening period) and after (the 'simplified' cascade screening period). The tertiary outcomes are demographic characteristics associated with uptake of cascade screening or uptake of preventative therapy.

Aim 2: A subset of 30 probands and 45 family members will undergo in-depth interviews in order to assess their perspectives on receiving the results and undergoing cascade screening. This aspect of the study is particularly important because of the nature of our pre-intervention/post-intervention study design. By gathering qualitative data on why participants did or did not undergo cascade screen we can discern whether it was the simplified screening approach or whether it was the second reminder to get screened, or some other aspect of the study design. Our interviews will assess how the return of results process impacted participants, how cascade screening impacted participants, why or why not participants chose to undergo screening, what were the barriers to undergoing screening, and why or why not participants followed recommendations for beta-blocker therapy.

ID: VIEW4E02805CF7000  
Name: v2\_Lay Summary

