Aim 1: Prior to the start of our intervention, all probands will be mailed a consent letter describing the study, a questionnaire, a response card and a copy of the family invitation letter. The questionnaire will capture data on the period of time since their return of results, including, the extent to which they shared results with family members, health behaviors (i.e. are they taking preventative therapy, if indicated) and how the results have impacted them. With the proband's permission, invitation letters will be mailed to their first degree relatives to offer study participation including the intervention (free, in-home, saliva-based genetic testing) and completion of questionnaires about their experiences with genetic testing. The proband can decide to enroll their minor children who still live at home in the cascade screening (Screening only for children under age 18 with specified consent/assent). We will offer the intervention for approximately 9 months, then we will repeat the mailed questionnaires assessing uptake, disclosure, health behaviors, and general impact of the intervention.

We will compare outcomes before the implementation of our intervention (the 'traditional' cascade screening period) and after (the 'simplified' cascade screening period). Our primary outcome addresses the question of whether our simplified cascade screening intervention improves uptake of screening. Our secondary outcomes assess whether, with access to simplified screening (1) probands will tell more family members, who may or may not choose to get screened, (2) informed family members are more likely to get tested, and (3) identifying more individuals with the KCNQ1 variant actually results in more beta-blocker prescriptions since the Amish typically take very few prescription medications. The tertiary outcomes are demographic characteristics associated with uptake of cascade screening or uptake of preventative therapy.

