These interviews will assess patient-reported impact of disclosure and impacts on health behaviors. They will also inform our understanding of why cascade screening of family members is or is not initiated and the extent to which cost and ease of testing (blood versus in-home saliva collection) impact screening uptake. By comparing rates of cascade screening before and after our intervention together with qualitative interviews, we can evaluate the extent to which ease, comfort, transportation issues, and cost impact the uptake cascade screening and improve our ability to apply the findings to appropriate comparable situations in clinical practice and in the most optimized manner.

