To date, 88 individuals have participated in a return of results study (ROR) for clinical confirmation of the mutation, collection of clinical information, genetic counseling, and recommendations for treatment. Genetic counseling included recommendations for all first degree relatives (who are at 50% risk of having the KCNQ1 mutation) to undergo genetic screening (cascade testing). This testing would involve going to the Clinic for Special Children and obtaining the genetic test via a blood sample for \$50 per test.

Cascade testing is considered to be a highly efficient procedure for identifying additional mutation carriers who might be helped through a preventive intervention. Despite the very clear potential clinical benefit of cascade testing, uptake has traditionally been low, particularly in the United States where active screening (i.e. direct contact of relatives) is not allowed due to privacy laws.

Understanding the impact of returning these results and initiating cascade screening of family members is critical for developing best practices and optimizing the processes. Most cascade screening studies to date have been conducted outside the United States where different laws exist regarding contacting family members. Therefore, our study will attempt to address a gap in knowledge regarding whether overcoming physical and financial barriers will improve uptake of cascade screening.

**4 \*Provide the scientific or scholarly background, rationale, and significance of the research and how it will add to existing knowledge:**

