For the interview portion of the study, participants (adults only) will be sampled purposively to include roughly 30 probands and 45 family members. In order to maximize variability with respect to the genetic test results (e.g., positive and negative), whether or not they shared their results, and primary implementation outcomes (e.g., whether or not they underwent cascade screening), we will enroll 15 probands who shared results with family members, 15 probands who did not share results, 15 family members who underwent cascade screening and were mutation positive, 15 family members who underwent cascade screening and were mutation negative, and 15 family members who did not undergo cascade screening. The goal of this sampling strategy was to achieve maximum variation and minimal informational redundancy. A guide for qualitative research is usually to include approximately 15 interviewees in order to obtain saturation and a homogeneous sample with maximum variation. Therefore, we expect to reach saturation and have a good representation of our participants.

**2 \* Provide the plan for data analysis. Include in the description the types of comparisons that are planned (e.g., comparison of means, comparison of proportions, regressions, analysis of variance, etc.), which is the primary comparison/analysis, and how the analyses proposed will relate to the primary purposes of the study:**

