## Recruitment

1 \* Describe plans for recruitment, including the identification of potential participants (or acquisition of charts/records/samples) and initial interactions with them: (If this study involves the VA please list all sites at which recruitment will take place.):  
Individuals who participated in the KCNQ1 ROR study (probands) and their first degree blood-related family members will be invited to participate. First degree family members of identified carriers will also be eligible for testing.

All probands who underwent the return of results process (n=88 to date) will be mailed an information / consent letter and response form (uploaded in Informed Consent Section), a questionnaire about their attitudes and experience with genetic testing (uploaded to Surveys Section), and a sample family invitation letter (uploaded below). These participants all agreed to recontact during the consent process for the study their KCNQ1 ROR was conducted under (see Retrospective Data Section). In the information/consent letter, probands will be asked to complete and return the questionnaire as an indication that they agree to join the study. They will be informed that they may be asked to participate in an in-person interview. The letter will also ask if we can invite their adult first-degree family members who live locally to take part in the study, whether or not the proband participates. They will be given the option to enroll their minor children (with appropriate consent and assent) in the free cascade testing portion of the study. The proband will complete and return the response form to indicate whether they agree to contact of family members.

With the proband's permission, the family invitation letter will be mailed to the first-degree family members of the proband using information from the 2009 Fisher Book and 2018 Address book of the Lancaster County Amish. At the proband's request, copies of the family invitation letter will, instead, be mailed to the proband so they can hand deliver them to family members of their choosing. The family invitation letter will explain our intervention offering free, mail-in, saliva testing of first degree family members.

2 \* Describe measures that will be implemented to avoid participant coercion or undue influence (if not applicable to the study, enter "N/A"):

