## Informed Consent Process

**If the study does not involve interaction with participants or a waiver of consent is being requested , answer "N/A" to the questions below.**

1 \* Indicate the type(s) of consent that will be involved in this study: (check all that apply)

- Not applicable (study may qualify as exempt)
- Request to Waive Consent/Parental Permission (Consent is not being obtained)
- Request to Alter Consent (Some Elements of Consent Waived)
- Request to Waive Documentation of Consent (Verbal/Oral Consent)
- Written Consent Form
- Electronic Consent

2 \* Describe the Informed Consent process in detail:

Family member consent process: Family members will be visited in their home after the ARC staff receives their response card expressing interest in testing, or possibly if no response is received. Participants will be approached by a study team member (usually a nurse) and an Amish liaison. The study will be briefly explained to the participant who will be asked if they would like to hear more about the study for possible participation. If they are unsure, information will be given with the name and phone # of the study team member to contact if they are interested in hearing more in the future. If the potential participant expresses interest in the study and invites the study team into their home, the study will be explained in detail using the consent form. The potential participant will be invited to ask questions throughout the process and will be reminded often that the study is voluntary. Ample time will be given to make a decision regarding participation in the study. If they decide to participate the consent form will be signed and dated by both the participant and the study team member.

We are requesting a Waiver of Documentation of Consent for probands and family members who decline genetic testing. These individuals will be mailed an information / consent letter along with a questionnaire.

3 \* Confirm that the consent process will explain the following:

- The activities involve research.
- The procedures to be performed.
- That participation is voluntary.
- The name and contact information for the investigator.

Yes  No

4 \* Describe who will obtain Informed Consent:

Designated, trained members of the research team will obtain informed consent.

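### The before-after design and purposive interviews cannot separate simplified testing from the renewed prompt, so the primary conclusion should be the effect of the whole package

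*Combined protocol and SAP*

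**What the plan says.** The protocol's Lay Summary (Aim 2) recognises that a pre/post design leaves the cause of any rise open. It says the interviews will settle this: "we can discern whether it was the simplified screening approach or whether it was the second reminder to get screened". Under Justification, Objective, & Research Design, item 2, a related claim is made for uptake rates and interviews together: "we can evaluate the extent to which ease, comfort, transportation issues, and cost impact the uptake cascade screening".

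The interview sample is set out in the protocol (Sample Size and Data Analysis, item 1) and again in SAP section A2: "participants (adults only) will be sampled purposively to include roughly 30 probands and 45 family members". The family quotas are 15 tested and mutation-positive, 15 tested and mutation-negative, and "15 family members who did not undergo cascade screening". SAP section B2 plans thematic coding in NVivo, stopping when the team agrees that nothing new is emerging.

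The primary outcome (SAP B1.1) is the proportion of eligible first-degree relatives tested before versus after. Both documents say that this difference cannot be compared statistically.

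**The concern.** The authors themselves name the rival explanation: relatives may come forward because they were asked again, not because the test became free and easy. Ruling that out needs either people who were prompted again but offered only the old test, or a design in which the two changes start at different times. The plan has neither. It offers interviews with a sample picked for variety, which can describe reasons but cannot show what a reminder alone would have produced.

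At stake is what the trial may conclude. The Research Design text intends to carry the findings into clinical practice. A reminder letter and a free home-testing service are very different programmes, and a rise in uptake credited to cost and convenience might owe part of its size to renewed contact.

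**Working it through.** **1. The plan's own figures.** 0.03 × 500 = 15; 500 − 15 = 485; 0.18 × 485 = 87.3, given as 87. At 7 children per proband, 15/7 = 2.1 and 87/7 = 12.4 probands, in line with the stated 2-3 and 12-13. The example reproduces: 15/500 = 3.0%, 87/485 = 17.9%, difference 14.9 points. No alpha or power is stated, so there is none to check.

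**2. What changes between the periods.**

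| | Traditional | Simplified |
|---|---|---|
| Prompt | Counselling of the proband: "Genetic counseling included recommendations for all first degree relatives" | Study letter |
| Reaches relatives through | The proband | Letter mailed with the proband's permission, or handed on by the proband (Study Procedures, item 1; SAP A1 mentions only the second route) |
| Further contact | None described | Home visit after a reply, "or possibly if no response is received" |
| Test | Blood sample at a clinic | Saliva or swab at home |
| Price | $50 | Free |

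By either route, the prompt and the offer are in the same letter: "The family invitation letter will explain our intervention offering free, mail-in, saliva testing of first degree family members" (Recruitment, item 1). Study Procedures describes home collection rather than mail-in, but that does not affect the argument.

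**3. Can the counts separate them?** Let *a* be baseline uptake, *r* the effect of renewed contact and *s* the effect of simplified testing.
- Before: *a* = 3.0%
- After: *a* + *r* + *s* = 17.9%
- Hence *r* + *s* = 14.9 points, and nothing more is known.

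The design rows are (1, 0, 0) and (1, 1, 1), which have rank 2 for three unknowns. Splitting the periods into months repeats these rows and leaves the rank at 2. The pairs (*r*, *s*) = (0, 14.9), (5.0, 9.9) and (14.9, 0) fit identically.

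**4. Can the interviews separate them?** No quota is set by period or by exposure to a reminder. Tested people fill 30 of the 45 family places (67%), against 18% tested after the intervention in the example, so the share giving a particular reason cannot be projected to relatives. No interviewee has experienced a second prompt with the old test only.

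**5. Would equal time windows separate them?** Let *p* be the effect of a recent first prompt and *d* the amount by which the second prompt differs from the first.
- Window after first counselling: *a* + *p*
- Later traditional time: *a*
- Window after the study letter: *a* + *p* + *d* + *s*

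This has rank 3 for four unknowns. The matched-window difference is *d* + *s*. It equals *s* only if *d* = 0 and there is no time trend.

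For scale, the intervention period is given ("We will offer the intervention for approximately 9 months"), but the length of the traditional period is not. As a labelled assumption only, take the existing-data range under Retrospective Data, 10/12/2015 to 10/31/2018, as its upper bound: 1,115 days / 30.4375 = 36.6 months.
- Tests spread evenly: 15 × 9/36.6 = 3.7 tests, or 0.7% of 500; matched difference 17.9 − 0.7 = 17.2 points.
- All 15 tests in the first 9 months: 3.0%; matched difference 14.9 points.

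Timing therefore carries some information about how relatives responded to the first prompt, but it does not isolate the second.

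**The case against.** The best reply is that the plan is more modest than one sentence suggests. The strongest claim sits in the Lay Summary and is not repeated in the SAP. SAP A2 gives the interviews the task of elaborating on Aim 1, and B2 plans thematic coding, with no proportion to be estimated. The study calls itself a pilot, disclaims a statistical comparison and names the second reminder openly. This stands as a reason to treat the matter as a limit on the conclusion rather than a failure of the trial. It does not remove the point, because the Research Design section, outside the lay summary, also claims to gauge how far each factor matters.

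A reader might infer that the interviews are the only safeguard. The documents do not support that. Secondary outcome (b), the proportion tested among relatives who were told, conditions on one route by which a reminder could act, and several questionnaires are planned. Still, a relative told in the later period also meets the new offer, so outcome (b) does not separate the two.

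A reader might also infer that dated chart data would settle the question at no cost. They would not, as step 5 shows. The two prompts also differ in recipient, mode and intensity. Charts are named as the source of the number screened (SAP B1.1). Collection dates are documented only for study saliva and swab samples (Prospective Samples, item 4). The retrospective fields listed are variant status and contact details (Retrospective Data, item 3), with no counselling or earlier test dates.

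**Conclusion.** The plan claims a property that its design lacks. On its own example, the 14.9-point rise belongs to renewed contact, letters to relatives, a free test and home collection jointly. Assuming that no component lowers uptake, the share due to simplified testing could be anything from 0 to 14.9 points. This rests on the prompt and the offer starting together and on there being no group or period with a reminder alone, and the documents show both.

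It would go too far to say that the reminder explains the rise, or that the interviews have no value. The documents give no evidence on how the rise divides, and stated reasons are useful supporting material on mechanism. Nor do the documents define 36.6 months as the traditional period: that is the range of existing data from other protocols, and families entered return of results at different times.

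**What to change.** 1. State the primary conclusion as the effect of the whole package: renewed contact plus free in-home saliva testing.
2. In the Lay Summary, replace the claim to discern the cause with a statement that the interviews explore participants' stated reasons. Revise Research Design, item 2, to match. State in both the protocol and the SAP that reminder and simplified testing remain confounded.
3. As a sensitivity analysis, where counselling, mailing and test dates can be retrieved, report uptake per proband family in equal windows of about 9 months after first counselling and after the study letter. Say that this removes unequal follow-up, that it helps bound the reminder explanation only if the two prompts act alike with no time trend, and that it does not separate the components. Relatives in the second window have also already been exposed to the first prompt.
4. Optionally, add a closed item on the main reason for testing or not testing to the family forms, after checking whether they already hold one; their contents are not shown.

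The cost is a narrower claim, edits to two protocol sections and the SAP, and some date extraction, probably from study logs as well as charts. Recruitment, procedures and sample size do not change.
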